11. PREGNANCY

WOCBP include any female who has experienced menarche and who has not undergone successful surgical sterilization (*e.g.*, hysterectomy, hysteroscopy, bilateral tubal ligation, bilateral oophorectomy or bilateral mini-laparotomy) or is not postmenopausal. Postmenopausal is defined as ≥ 12 months with no menses without an alternative medical cause. Women who are WOCBP and are using an active method of birth control, are practicing abstinence or where the partner is sterile (*e.g.*, vasectomy), should be considered to be WOCBP.

All WOCBP must use an active method of birth control during the course of the study, in a manner such that risk of failure is minimized. Abstinence or having a sterile partner is not an active method of birth control.

Prior to trial enrollment, WOCBP must be advised of the importance of avoiding pregnancy during trial participation and the potential risk factors for a pregnancy. The subject must sign an informed consent form documenting this discussion. During the trial, all WOCBP will be instructed to contact the investigator immediately if they suspect they might be pregnant (*e.g.*, missed or late menstrual period).

If a subject or investigator suspects that the subject may be pregnant prior to study medication administration, the study medication must be withheld until the results of a pregnancy test are available. If pregnancy is confirmed, the subject must not receive study medication and must be discharged from the study.

If, following study medication administration, it is determined that the subject may have been or was pregnant at the time of study medication exposure (including at least 2 days after study medication administration) the investigator must immediately notify the Medical Monitor and record the event on a pregnancy surveillance form. While not an AE or SAE, the investigator must report every pregnancy using a pregnancy surveillance form and follow the reporting procedures described for SAE reporting (Section 10.2.2).

Protocol-required procedures for trial discontinuation and follow-up must be performed on the subject unless contraindicated by pregnancy (*e.g.*, x-ray studies). Other appropriate pregnancy follow-up procedures should be considered if indicated. In addition, the investigator must report to the Medical Monitor on the pregnancy surveillance form, follow-up information regarding the course of the pregnancy, including perinatal and neonatal outcome. Infants should be followed for a minimum of six weeks.

12. STATISTICAL CONSIDERATIONS

12.1. Sample Size and Power Consideration

Based on results from a previous study with similar design, the expected standard deviation for the primary efficacy parameter is approximately 23.7%. The mean difference between the two Active treatment groups is expected to be approximately 10 percentage points. With approximately 250 randomized subjects this study is expected to achieve approximately 85% power for the comparison between the two Active treatment groups, and more than 95% power for the pair-wise comparisons between each Active treatment group and the Vehicle group. Two-tail alpha will be set to 0.05 for all comparisons.

12.2. Statistical Analysis of Efficacy

The primary effectiveness analysis will consist of pair-wise comparison between each active treatment group and the vehicle treatment group, and between the two active treatment groups, based on the mean of per-subject percentages of target lesions judged to be clear on the PLA (PLA = 0) at Visit 8. To conduct this analysis, the percentage of each subject's target lesions judged to be clear on the PLA at Visit 8 will first be calculated for each subject. Then the analysis will calculate the mean of this parameter for each treatment group (yielding an estimate of the mean percentage of clear lesions across subjects), and an analysis of variance (ANOVA) model will be used to perform all pair-wise comparisons among the treatment groups. Pair-wise comparisons will be conducted on the least-squares means using the overall pooled error term of the model. All efficacy analyses will be based on the per protocol (PP) population, defined as all randomized subjects who completed the study with no major protocol violation.

A secondary effectiveness analysis will be conducted using the same methodology as the primary efficacy analysis based on the mean of per-subject percentages of target lesions judged to be clear or near-clear on the PLA (PLA \leq 1) at Visit 8. The primary and secondary analyses above will also be conducted separately for lesions in each body location, using the same methodology as specified above.

In addition to the above Visit 8 analyses, each of these analyses will be conducted at each other visit where PLA scores are collected, as exploratory analyses.

Three exploratory responder analyses will be conducted using the following criteria for classifying subjects as responders:

- Subjects with PLA = 0 for all 4 target lesions at Visit 8;
- Subjects with PLA = 0 for at least 3 target lesions at Visit 8; and
- Subjects with PLA \leq 1 for all 4 target lesions at Visit 8.

For each exploratory analysis, separate chi-square tests will be used to compare the percentage of responders between each active treatment group and the vehicle treatment group, and between the two active treatment groups. The chi-square analyses may be supplemented by one logistic regression model for each exploratory analysis that will allow all 3 pairwise comparisons to be performed within a single model.

Duration of response will be calculated on a lesion basis by determining the percentage of clear lesions (PLA=0) at Visit 8 which remain clear at Visit 13. This will be done for each treatment group separately.

For all analyses, two-tail alpha will be set to 0.05 with no adjustment for multiple comparisons. ANOVAs will include Site in the model if doing so improves the sensitivity of the model for comparing treatment groups.

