8.1.2. Physician's Lesion Assessment (PLA)

The PLA is the investigator's assessment of the severity of the Target Lesion at a particular time point. The investigator should NOT refer to any other assessments to assist with these assessments.

At Visits 1, 2, 4, 6, 7 and 8, the investigator will assess the Target Lesion using the scale below and report the one integer that best describes the severity of the Target Lesion. At Visit 2, and if appropriate Visit 4, the investigator must complete the PLA prior to the study medication treatment.

Table 3 Physician's Lesion Assessment Definitions

Physician's Lesion Assessment	
Grade	Descriptor
0	Clear: no visible seborrheic keratosis lesion
1	Near Clear: a visible seborrheic keratosis lesion with a surface appearance different from the surrounding skin (not elevated)
2	Thin: a visible seborrheic keratosis lesion (thickness ≤ 1 mm)
3	Thick: a visible seborrheic keratosis lesion (thickness > 1 mm)

All investigational site staff will receive training on the PLA Assessment Scale and be provided with a PLA Assessment Manual (refer to Appendix 15.2) that will be used as a reference tool during the conduct of the study.

In order for a subject to be eligible for screening and randomization to the study, each Target Lesion must have a PLA grade of ≥ 2 .

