8.1.3. Lesion Dimensions

At Visit 1 and at Visit 2 prior to randomization the investigator will measure the length and the width of each Target Lesion using the ruler provided.

The investigator must measure the length and width of each Target Lesion in millimeters (mm) as follows:

- Length (*i.e.*, the length of the longest axis) reported to the nearest mm
- Width (*i.e.*, the length of the longest axis perpendicular to the length) reported to the nearest mm.
- Thickness (height above the surrounding skin)

At Visit 1 for the subject to be enrolled and at Visit 2 for the subject to be randomized each Target Lesion must have:

- A Length that is $\geq 5\text{mm}$ and $\leq 15\text{mm}$
- A Width that is $\geq 5\text{mm}$ and $\leq 15\text{mm}$.
- A Thickness that is $\leq 2\text{ mm}$.

At Visit 2, the length and width must be measured prior to any study medication treatment.

At Visits 1, 2, 4, 6, 7 and 8 the investigator must measure the thickness (height) of each Target Lesion above the surrounding skin, in mm using the ruler provided as part of the PLA assessment.

At Visit 1 for the subject to be enrolled, each Target Lesion must have a thickness that is $\leq 2.0\text{mm}$.

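### The primary ANOVA adjusts for no baseline lesion characteristic, which may give up modest precision on the 45% versus 40% comparison

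*Combined protocol and SAP*

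**What the plan says.** Section 12.2 takes each subject's percentage of Target Lesions with PLA = 0 at Visit 8 and says that "an analysis of variance (ANOVA) model will be used to perform all pair-wise comparisons among the treatment groups". It adds: "Pair-wise comparisons will be conducted on the least-squares means using the overall pooled error term of the model". The secondary analysis (PLA of 1 or less) uses the same method, and both are repeated by body location. The only further model term is conditional: "ANOVAs will include Site in the model if doing so improves the sensitivity of the model for comparing treatment groups".

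The baseline information is already collected:

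- **PLA grade** (section 8.1.2): "At Visits 1, 2, 4, 6, 7 and 8, the investigator will assess the Target Lesion using the scale below". At Visit 2 it must be completed before treatment.
- **Length and width** (section 8.1.3): "At Visit 1 and at Visit 2 prior to randomization the investigator will measure the length and the width of each Target Lesion". Thickness is measured at Visits 1 and 2 as part of the PLA.
- **Body area** of each lesion (section 8.1): recorded in the CRF when Target Lesions are identified at Visit 1.

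Section 7.2 gives a 1:2:2 allocation and names no stratification factor.

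**The concern.** Lesions differ at entry. PLA may be 2 or 3, thickness goes up to 2 mm, and one to three of the four lesions may be facial. The PLA grades presence and thickness, so baseline PLA is the starting value on the endpoint's own scale. If starting grade or location predicts clearance, a treatment-only model leaves that variation in the error term, and nothing in the design balances lesion mix between arms.

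The comparison most exposed is 45% versus 40%. Its stated power is about 85%, against more than 95% for each comparison with vehicle.

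**Working it through.** **Inputs from the documents.** Section 12.1: "the expected standard deviation for the primary efficacy parameter is approximately 23.7" percent; "The mean difference between the two Active treatment groups is expected to be approximately 10 percentage points"; "Two-tail alpha will be set to 0.05 for all comparisons". Synopsis: 100 subjects per active arm and 50 on vehicle. The pooled error term has 250 - 3 = 247 degrees of freedom.

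**Step 1: the plan's own figure.** The standard error of the difference is 23.7 × √(1/100 + 1/100) = 3.35. The noncentrality is 10 / 3.35 = 2.98. Power from the noncentral t on 247 df is 84.4% (84.7% by the normal approximation). The stated 85% reproduces.

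**Step 2: power with adjustment.** Let R² be the share of within-arm variance that the covariates explain. With q covariates, the error variance becomes 23.7² × (1 - R²) × (1 + q/(247 - q)) on 247 - q df. The last factor charges for chance covariate imbalance. For q = 3 it is 1 + 3/244 = 1.0123.

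| Assumed R² | Effective SD | Noncentrality | Power | Change from 84.4% |
|---|---|---|---|---|
| 0 | 23.85 | 2.97 | 84.0% | -0.4 |
| 0.016 | 23.65 | 2.99 | 84.6% | +0.2 |
| 0.05 | 23.24 | 3.04 | 85.8% | +1.4 |
| 0.10 | 22.62 | 3.13 | 87.6% | +3.2 |
| 0.137 | 22.15 | 3.19 | 88.9% | +4.5 |

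Changes are differences of the rounded figures. Adjustment pays when (1 - R²)(1 + q/(247 - q)) is below 1, that is, when R² exceeds about q/247. That is 0.012 for three covariates. For the two covariates recommended here it is 0.008, and power at R² = 0 is 84.1%, so the three-covariate table is slightly conservative.

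**Step 3: which R² is plausible?** The documents give none. If clearance differs by g points between two lesion types, one more lesion of the harder type moves a subject's expected percentage by g/4. One covariate then explains R² = (g/4)² × V / 23.7², where V is the variance of the lesion count. All values of g and V here are assumptions:

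- g = 20 for face versus trunk or extremities, V = 0.5 to 1.0: 25 × 0.5 / 561.7 = 0.022, up to 25 × 1.0 / 561.7 = 0.045.
- g = 20 for PLA 3 versus PLA 2, V = 1 to 2: 0.045 to 0.089.
- g = 10, V = 1: 6.25 / 561.7 = 0.011, about break-even.

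A lesion-level simulation with gaps of 10 to 25 points on both factors, 40% of lesions thick, one to three facial lesions and within-subject correlation 0.1 to 0.3 gave R² from 0.016 to 0.137, the range in the table. With 5-point gaps, R² was only 0.003 to 0.004.

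**Step 4: chance imbalance.** The 95% range of the shift in the 45% minus 40% difference due to covariate imbalance is 1.96 × √R² × 23.7 × √(2/100). That is ±1.5 points at R² = 0.05 and ±2.4 at 0.137, against an expected 10-point effect.

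**The case against.** The strongest reply is that this is a preference. Under randomization the unadjusted ANOVA is unbiased, its type I error already allows for chance imbalance, and the protocol claims only the power that this analysis delivers. All of that stands. A reader might infer that the primary analysis is wrong or the trial mis-powered; the documents support neither.

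A reader might also infer that adjustment gives free precision. It does not: covariates that predict nothing cost a few tenths of a point of power, and with 5-point clearance gaps adjustment is a very small net loss. The entry criteria narrow both covariates, which limits the gain. Powers above 90% would need R² near 0.20, beyond what the simulated scenarios produced.

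Two further inferences go too far. The by-location analyses do not show that location is thought to be prognostic. Section 12.2 gives no reason for them, and section 2.1 describes earlier dose-ranging studies run separately on trunk/extremities and on the face, so reporting by site is an equally natural explanation. Nor is there a case for adding lesion area: it is recorded, but no gain from it has been shown.

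What survives is an asymmetry. The possible loss is small and bounded, the possible gain is larger, and the data are already collected.

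**Conclusion.** A cheap improvement, not a correction. The plan leaves out baseline lesion characteristics that it collects, and so may give up modest precision on its least-powered comparison. On the plan's SD, difference and arm sizes, the change in power is about -0.4 to +4.5 points for R² from 0 to 0.137. R² is an assumption throughout, and the documents cannot narrow it.

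**What to change.** Before unblinding, specify in section 12.2 and the SAP an ANCOVA with treatment and two fixed covariates:

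- the number of Target Lesions at PLA 3 at Visit 2, before treatment;
- the number of facial Target Lesions, as identified at Visit 1.

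Use it for both Visit 8 analyses (PLA = 0 and PLA of 1 or less). Report adjusted least-squares mean differences with 95% confidence intervals, and keep the unadjusted ANOVA as a sensitivity analysis. Omit the facial count from the by-location models, because there it is the denominator of the face-only outcome. Name the PLA 3 count alone, with no alternative thickness measure, so that no choice is left open in the primary model.

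The cost is two degrees of freedom and at most about 0.4 point of power if the covariates are uninformative. No new data, visits or subjects are needed. Section 12.2 is protocol text, so the change needs a written amendment under section 13.1 as well as SAP wording.

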1. SYNOPSIS

Protocol Number A-101-SEBK-204 Synopsis	
Protocol Number:	Protocol Title: A Phase 2 Randomized, Double-Blind, Vehicle-Controlled, Parallel Group Study of the Safety and Effectiveness of A-101 (hydrogen peroxide) Topical Solution in Subjects with Seborrheic Keratosis Lesions on the Trunk, Extremities and Face
Sponsor: Aclaris	Phase of Development: Phase 2
Study Drug Description: A-101 Solution (40% and 45%) is a hydrogen peroxide solution that will be supplied in a glass ampule with an applicator to be applied to seborrheic keratosis lesions of the trunk, extremities and face.. The study drug, A-101 (hydrogen peroxide) 40% and 45% Topical Solution (hereafter referred to as A-101) is a colorless solution that must be stored at room temperature (20-25° C or 68 -77 ° F), protected from light.	
Study Objectives: Primary: The main objective of this study is to evaluate the effectiveness of A-101 40% and A-101 45% versus vehicle for the treatment of 4 seborrheic keratosis (SK) Target Lesions on the trunk, extremities and face. Secondary: The secondary objectives of this study include: 
 • Duration of response • Safety 	
Study Design: This is a phase 2, multicenter, randomized study to evaluate the safety and efficacy of A101 40% and A101 45% versus vehicle. Subjects will be required to have a total of 4 target seborrheic keratosis (SK) lesions located on their trunk, extremities and face. At least one of the 4 target lesions must be on the face and at least one of the target lesions must be on the trunk or extremities. Subjects will be randomized to one of 3 treatment arms in a 1:2:2 ratio. Fifty subjects will be randomized to the Vehicle treatment arm and 100 subjects will be randomized to each A-101 active treatment arm. Subjects will receive a maximum of 2 treatments [Day 1 (Visit 2) and re-treatment on Day 22 (Visit 4) if a target lesion meets the criteria for re-treatment]. The duration of study participation is anticipated to be up to a maximum of 124 days per subject. Safety will be evaluated based on clinical laboratory studies (hematology and clinical chemistry), vital signs, assessment of local skin reactions (LSRs), assessment of adverse events (AEs), and concomitant medication review.	

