2.2. Summary of Previous Clinical Trials with A-101 Solution in Seborrheic Keratosis

2.2.1. A-101-SEBK-301

A-101-SEBK-301 was a randomized, double-blind, vehicle-controlled, parallel-group study of A-101 and vehicle to investigate the effectiveness, safety, and tolerability in subjects with SK target lesions on the trunk, extremities, and face. Subjects randomized to the study were able to receive up to 2 applications of A-101 40% or matching vehicle.

A total of 450 subjects were randomized and 435 (96.7%) completed the study. Among the 15 subjects who discontinued, the reasons were similar between the treatment groups with the most frequent being a protocol violation (2.6% vehicle, 2.2% A-101). Two subjects (0.4% vehicle, 0.4% A-101) discontinued due to an AE or SAE. The mean age was 68.7 years (range 42 to 90, 42.0% were at least 71 years old), 41.3% of subjects were male and 58.7% were female, and 97.8% were Caucasian. The most common Fitzpatrick skin types were 2 (46.9%) and 3 (27.3%).

Treatment with A-101 40% showed statistically significant efficacy compared to treatment with vehicle based on the primary analysis.

For the primary endpoint, the proportion of ITT subjects who achieved clearance (PLA = 0) of all 4 target lesions at Visit 8 (Day 106) was 4.0% with A-101 compared to 0.0% with vehicle ($p = 0.0019$). For the secondary endpoint, the proportion of ITT subjects who achieved clearance of at least 3 of the 4 target lesions at Visit 8 was 13.45% with A-101 compared to 0.0% with vehicle ($p < 0.0001$).

Treatment Emergent Adverse Events (TEAEs) were reported for 45 (19.8%) subjects in the vehicle group and 54 (24.2%) subjects in the A-101 group. The most frequently reported TEAEs were nasopharyngitis (3.1% vehicle, 1.3% A-101), bronchitis (0.4% vehicle, 1.3% A-101), and upper respiratory tract infection (1.3% vehicle, 0.4% A-101). Six (2.6%) subjects in the vehicle group had 8 SAEs and 4 (1.8%) subjects in the A-101 group had 4 SAEs. The SAEs were all considered not related to study medication. Two subjects, 1 in each treatment group, discontinued the study due to an SAE.

LSRs were few and predominantly mild. The LSRs of pruritus and stinging reported by subjects and crusting, edema, erythema, hyperpigmentation, scaling, and vesicles reported by the investigator following treatment and retreatment had generally resolved by Visit 8 (Day 106).

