3.2. Study Objectives

3.2.1. Primary Objective

The primary objective of this study is to evaluate the safety and effectiveness of A-101 45% compared to A-101 40% and each active treatment arm to Vehicle for the treatment of 4 seborrheic keratosis (SK) Target Lesions on the trunk, extremities and face. For each subject, at least 1 Target Lesion must be on the face and at least 1 Target Lesion must be on the trunk or extremities.

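### Pooling the error over all three arms probably lets the nominal 5% test of 45% vs 40% run at about 6–8% (minor; depends on a vehicle SD that is not given)

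*Combined protocol and SAP*

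**What the plan says.** Section 12.2 and the statistical methods in the synopsis put all three arms into one ANOVA on the per-subject percentage of clear target lesions at Visit 8. For the error they state: "Pair-wise comparisons will be conducted on the least-squares means using the overall pooled error term of the model". No section provides for unequal variances, a variance check, or an error term taken from the active arms alone. Section 12.2 uses the same method for the secondary endpoint (clear or near clear), for each body location, and for the other visits with PLA scores. Alpha is two-sided 0.05 for every comparison, without multiplicity adjustment. Site may be added if that makes the model more sensitive.

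The allocation is unequal: "Fifty subjects will be randomized to the Vehicle treatment arm and 100 subjects will be randomized to each A-101 active treatment arm" (synopsis, Study Design). Section 12.1 gives a single SD, "the expected standard deviation for the primary efficacy parameter is approximately 23.7" percent, and "approximately 85% power for the comparison between the two Active treatment groups".

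The weight given to 45% vs 40% differs by section. Section 3.2.1 names it first ("evaluate the safety and effectiveness of A-101 45% compared to A-101 40% and each active treatment arm to Vehicle"), while the synopsis objective names only the vehicle comparisons ("evaluate the effectiveness of A-101 40% and A-101 45% versus vehicle"). Section 12.2 makes it one of three primary comparisons.

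**The concern.** A pooled error term is right for every pair only if all arms share one variance. Here the outcome takes the values 0, 25, 50, 75 and 100%, and an arm where almost nothing clears has little room to vary. Section 2.2.1 reports that clearance of at least three of four lesions "at Visit 8 was 13.45% with A-101 compared to 0.0% with vehicle". Section 2.2.2 reports 23.0% against 0.0% for the same measure in study 302.

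If the vehicle variance is the smaller one, vehicle subjects pull the pooled error below the true active-arm error. The 45% vs 40% standard error is then too small and its p-value too favourable, while the vehicle comparisons move the other way. The gain therefore falls on the comparison with the least planned power (85%, against more than 95%), where a borderline result is most plausible. The question of whether 45% adds anything to 40% is also what motivates the trial in section 3.1.

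**Working it through.** **Inputs.** Arms of 50/100/100 (synopsis); SD 23.7, difference 10 points, two-sided 0.05 (section 12.1); pooled error (section 12.2). The ratio r = vehicle SD / active SD is not in the documents, so it is varied from 1 to 0.

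**The plan's own power figure.** SE = 23.7 × √(2/100) = 3.35, and the noncentrality is 10/3.35 = 2.98. Noncentral t power is 84.4% with 247 error df (three arms) and 84.4% with 198 (two active arms). The stated 85% is reproduced if 23.7 is the active-arm SD, and the vehicle arm's 49 df add essentially nothing.

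**Size of the 45% vs 40% test.** The expected pooled variance, relative to the active variance, is s = (198 + 49r²)/247. The nominal critical value is t(0.975, 247) = 1.970, so the actual size is approximately 2 × P(t₁₉₈ > 1.970 × √s). A result whose correct p is 0.05 (t = 1.972 on 198 df) prints as 2 × P(t₂₄₇ > 1.972/√s).

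**Vehicle comparisons.** The ratio of the pooled SE to the correct SE is √[s × 0.03/(0.01 + 0.02r²)], with 0.03 = 1/100 + 1/50. The size is 2 × [1 − Φ(1.970 × that ratio)].

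| r | s | SE shortfall, 1 − √s | Size, 45% vs 40% | Correct p of 0.05 prints as | SE ratio, active vs vehicle | Size, active vs vehicle |
|---|---|---|---|---|---|---|
| 1 | 1.000 | 0% | 5.0% | 0.050 | 1.00 | 4.9% |
| 0.87 | 0.952 | 2.4% | 5.6% | 0.044 | 1.07 | 3.6% |
| 0.75 | 0.913 | 4.4% | 6.1% | 0.040 | 1.14 | 2.5% |
| 0.5 | 0.851 | 7.7% | 7.1% | 0.034 | 1.30 | 1.0% |
| 0 | 0.802 | 10.5% | 7.9% | 0.029 | 1.55 | 0.2% |

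**Simulation check.** Normal data, 100,000 trials per ratio: pooled size 5.0%, 6.1%, 7.0%, 7.6% and 8.0% at r = 1, 0.75, 0.5, 0.25 and 0; with an active-arms-only error term, 4.9–5.0% throughout. Discrete 0/25/50/75/100% data (beta-binomial, assumed means of 25–30% active and 2–10% vehicle, r = 0.32–0.59), 60,000 trials per case: pooled 6.7–7.7%, active-arms-only 5.0%.

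**How likely is a small r?** Arm sizes in the two earlier studies follow from the adverse-event counts and the totals. Study 301 reports "45 (19.8%) subjects in the vehicle group and 54 (24.2%) subjects in the A-101 group": 45/0.198 ≈ 227 and 54/0.242 ≈ 223, which sum to the 450 randomized. In study 302, 43/0.177 ≈ 243 vehicle subjects, which leaves 487 − 243 = 244 on A-101. One subject in 227 or 243 would print as 0.4%, so 0.0% means none among 227 + 243 = 470. The 95% upper bound on the true proportion is 1 − 0.05^(1/470) = 0.64%. Under a beta-binomial model with within-subject correlation between about 0 and 0.3 (assumption), that bound limits the vehicle SD to about 9–16 points, or 0.39–0.69 of 23.7.

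**The case against.** **The premise is inferred.** No vehicle SD is stated, and the evidence is tail percentages only. Values of 0, 25 and 50% alone do not force a small spread: half the subjects at 0 and half at 50% gives an SD of 25, above 23.7. The 9–16 point bound needs a model. This stands, and it is why the conclusion is conditional.

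**The effect is small.** It is 1–3 points on one comparison in a phase 2 trial that openly declines multiplicity adjustment. Three unadjusted tests already give about 12% family-wise error under the global null (simulated, equal variances). A pooled ANOVA error is conventional and was specified in advance. This stands too and sets the severity. It does not remove the point, because declining to adjust across tests is a different choice from letting a single 5% test run above 5%.

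**The evidence covers only complete clearance at Visit 8.** Nothing in the documents shows unequal variances for the clear-or-near-clear, body-location or other-visit analyses. This stands; extending the fix to them is for consistency.

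**Two stronger readings are not supported.**

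- A reader might infer that 23.7 cannot be the active-arm SD, so that the 85% power is overstated. Study 301's reported tails (4.0% with four lesions clear, 13.45% with at least three) leave 86.55% of A-101 subjects free among 0, 25 and 50%, so the active SD could be anywhere from about 12 to 32. For study 302 (7.8% and 23.0%) the range is about 15 to 36. The figure 23.7 lies inside both, and read as the active-arm SD it reproduces the plan's power.
- A reader might also speak of miscalibrated confidence intervals, but no interval for a treatment difference is planned. The effect is on the tests.

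**Conclusion.** The point holds in conditional form and is minor. The pooled error term gives the 45% vs 40% test its nominal 5% size only if vehicle subjects vary as much as active subjects. The documents make a smaller vehicle SD likely but do not state one. For a ratio of 0.75 down to 0 the true size is about 6.1% to 7.9%; at 0.87 it is 5.6%, and at 1 there is no problem. The active-vs-vehicle tests are conservative over the same range. Only a borderline 45% vs 40% result would change: a correct p of 0.05 would print as 0.040 down to 0.029.

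These figures assume arms of 50/100/100, equal SDs in the two active arms and no Site term. With 47/95/95 in the per-protocol population (assumption) the sizes are also 6.1–7.9%. This is a cheap improvement to a primary comparison, not a demonstrated error in the plan.

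**What to change.** In section 12.2 and the synopsis, replace the pooled-error sentence with: *The 45% vs 40% comparison will use an ANOVA on the two active arms only, and each active arm will be compared with vehicle by a test that allows unequal variances (Welch/Satterthwaite).* Apply it to every analysis that uses the same methodology.

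State how Site is handled if it is included: for example, as a factor in the active-arms ANOVA and in an unequal-variance model for the vehicle comparisons. The text should also cover a vehicle arm in which every subject has the same value. A Welch test can still be computed then, with the SE coming from the active arm alone, but it has no Site term.

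The cost is a change of wording. The 45% vs 40% p-value becomes slightly less favourable when the vehicle SD is the smaller one. Power for that comparison is 84.4% with 198 or 247 error df at an SD of 23.7, so giving up the vehicle arm's degrees of freedom costs essentially nothing.
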